Statistical Analysis Plan

Official Title: Can Blocking the Orexin System Enhance Sleep's Benefits to Therapeutic Exposure for PTSD?

NCT number: NCT02849548

Date of the Document: July 7,2016

Data Analysis Plan: Initially, data will be pre-screened for errors, outliers, normality of distributions, and any necessary modifications such as transformation will then be conducted. The suvorexant and placebo groups will be compared on demographics and baseline measures using *t*-tests or chi-squared tests to examine group comparability. Fig. 1 describes each hypothesis. **Hypothesis 1a:** The primary comparison will be between the 2 groups (suvorexant vs. placebo) and sleep parameters measured at 3 time points (baseline, post-Session 1, and post-Session 3). A repeated-measures ANOVA will be performed to examine whether there is a Group x Time interaction effect on each sleep parameter of interest (i.e., N3, WASO, and REM sleep). If a significant interaction effect is found, group comparisons will be performed at each time point. **Hypothesis 1b:** A repeated-measures ANOVA will be performed to examine whether there is a Group x Time interaction effect on CAPS scores. In addition, 2(Group) x 2(Time) ANOVAs will be performed to examine if there is an interaction effect on intersession habituation between Session 1 & 2 and between Session 3 & 4, using a baseline-corrected highest average pulse rate as a dependent variable. **Hypothesis 1c:** To examine indirect effects of suvorexant on PTSD through the mediator, post-WNE sleep change, a path analysis using bootstrapping procedures will be performed for each sleep parameter of interest using SPSS macros developed by Preacher & Hayes.⁷⁰ Baseline CAPS scores will be included as a covariate. The same method will be used to examine indirect effects of suvorexant on intersession habituation.

Power considerations. G*Power⁷¹ was used to perform power analysis. $\alpha = .05$ was applied in all analyses. We estimate that 54 participants (27 in each group) will complete protocol (see the Feasibility section). **Hypothesis 1a:** The primary outcomes for power evaluation are WASO and REM sleep. The prior studies suggest small effects of suvorexant on N3; therefore, it was not considered for power evaluation. Herring et al's clinical trials^{48,50} showed that effect sizes of one night of 20/15mg suvorexant on WASO and REM sleep (minutes and %) were $f = -0.37$, 0.32, and 0.22, respectively. A total of 16, 22, and 50 participants are needed to detect a Group x Time effect on WASO and REM sleep in minutes and percentage, respectively, with 80% power. Since no studies have examined effects of suvorexant on PTSD, power analysis for **Hypothesis 1b** is based on effect sizes found in Taylor et al's⁴⁴ clinical trial of prazosin in civilian outpatients with PTSD. 12 participants are needed to detect the effect size found in this trial ($f = 0.40$). **Hypothesis 1c:** Sizes of the indirect effects of suvorexant on PTSD and intersession habituation through post-WNE sleep change are unknown. We selected the bootstrapping procedure as it is more powerful than Sobel test.⁷²

The proposed study also includes comparisons of several other variables. The relative sample size required for multiple comparisons of variables (between 10-20) allowing for Bonferroni-adjusted test to achieve 80% power relative to the sample size required for a nominal is only 3.⁷³ The proposed sample size of 54 will, therefore, have adequate power to detect medium to large effects in our planned analyses. Statistical significance of effects and their clinical importance will be carefully considered in data interpretation to inform the development of subsequent grant applications.

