Design and Overview (Table 3): This is a randomized, double-blind, placebo-controlled trial examining the effects of suvorexant (Merck & Co., Kenilworth, NJ), a dual orexin receptor antagonist that is FDA approved for insomnia, on sleep and PTSD symptom reduction following WNE. We will employ our successful recruitment strategies, including flyers, outreach activities, and referral from previous participants. Potential participants will initially be screened over the phone or in person, and those who meet initial criteria will be invited to the Clinical Research Unit (CRU) at Howard University to complete a consent procedure, questionnaires, a clinical interview, a physical examination, and urine tests. Participants who meet the selection criteria will be invited to complete two pairs of 30-minute WNE sessions and four overnight PSG recordings [screening, baseline, between WNE sessions (twice)]. Both pairs of WNE sessions will occur at 8PM and 8AM in the following morning with intervening sleep. The second pair will occur one week after the first pair. Four WNE sessions are

Table 3. Study Design

Day	1	2	3	4	5	11	12	18
Consent; Questionnaires	X							
Physical exam	X							
Vital signs	X				X		X	
Urine tests	X							
CAPS (lifetime & past month)	X							
SCID	X							
CAPS (past week)				X	X		X	
C-SSRS	X			X	X		X	
Alertness scale				X	X		X	
Adverse event assessment	X			X	X	X	X	
WNE (AM)					X		X	
WNE (PM)					X		X	
Suvorexant or placebo					X		X	
PSG		X screen	X baseline		X		X	

needed because the majority of participants in the preliminary study did not achieve remission until after completing the second pair of WNE. Participants will be stratified by gender and randomly assigned to either suvorexant or placebo. After the 1st evening WNE, a 10 mg tablet of suvorexant or placebo will be administered orally 30 minutes before bedtime. If the medication is well tolerated, the dose will be increased to 20 mg at the 2nd administration after the 3rd WNE. The recommended dose is 10mg, and the maximum recommended dose is 20mg.⁶⁰ The 1-week CAPS will be administered before the 1st and 3rd sessions and at 1-week follow-up.

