Feasibility: The primary mentor's lab has been successfully recruiting, on average, one trauma-exposed participant/week. A pilot study will be conducted during the current KL2 to address potential barriers for recruitment and retention of participants. In the R21 funded study, approximately a half of participants met inclusion criteria and completed at least first two WNE sessions (Fig. 2). Therefore, we expect to enroll 140 participants during the 40-month K01 recruitment period (3.5/month), and ~70 of them would complete at least first two WNE sessions. Based on the previous retention rate, we estimate that 54 participants (27 in each group) would complete the entire protocol. Reasons for dropouts from the R21 study included time conflicts and a family emergency. No participants reported distress related to WNE as a reason for withdrawal.

Assessment: Screening and self-report measures. The initial phone screening will include questions about excluded conditions, trauma exposure, and PTSD symptoms (using the Primary Care PTSD screen,⁶¹ a 4-item screener). The questionnaire package includes a demographic questionnaire, the Life Event Checklist (LEC)⁵⁵ to determine the most stressful event (the index trauma), and a sleep questionnaire developed in the mentor's lab to assess habitual sleep schedule and signs of possible narcolepsy.

Medical/physical tests. Vital signs, height, and weight will be measured, and a physical examination will be performed by a physician or a nurse practitioner. Urine toxicology screening (all participants) and a urine pregnancy test (all female participants) will be conducted by a nurse at the CRU.

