Clinical interviews. Structured interviews will be conducted by clinically trained staff and will be reviewed weekly in a consensus conference with the candidate (a licensed psychologist) and the primary mentor (a board certified psychiatrist). The CAPS⁵⁵ will be administered to assess current (past month and past week) and lifetime PTSD diagnosis and severity associated with the index trauma. The Structured Clinical Interview for DSM-5 (SCID)⁶² will be administered to assess current and lifetime psychiatric diagnoses and confirm inclusion criteria. The C-SSRS⁶³ will be administered at the initial visit to assess suicidal ideation and behaviors in lifetime and past 6 months and at subsequent visits to assess any changes since the previous visit. The PI will be immediately notified if a participant indicates concerning suicidal ideation or behaviors.

Sleep recordings. PSG recordings in the CRU will use a Natus/Embla (Pleasanton, CA) Titanium PSG unit including two central, frontal, and occipital EEG leads, two electrooculograms, chin and limb electromyograms, and an electrocardiogram. Participants will be instructed to go to bed at their habitual bedtime and wake up at 8 AM. Screening for sleep disordered breathing will be performed using the screening night data. Visual scoring of sleep records will be done following the American Academy of Sleep Medicine Manual, Version 2.3.⁶⁴ We will calculate standard PSG sleep parameters including total sleep time, WASO, the percentage and the duration of each sleep stage, and REM density using the REMLogic software (Natus/ Embla). Sleep changes from baseline to post-WNE will be computed by subtracting baseline measures from respective measures obtained during sleep following the 1st and 3rd WNE sessions.

Alertness visual analogue scale (VAS). Participants will complete an alertness VAS upon awakening in the morning after PSG recordings. The VAS is a 100 mm horizontal line with a label "very sleepy" on the left end and "very alert" on the right end. Participants will be place a

slash mark on the scale to indicate their alertness at the moment. A morning WNE session will not begin until the participant's alertness level reaches the level he/she indicated in the morning after the baseline PSG recording.

Adverse event assessment. Participants will be queried regarding the presence of any symptoms or concerns before and after the medication administration.

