Study Medication Administration: Participants will be stratified for gender and randomly assigned to either suvorexant or placebo before the 1st WNE. Suvorexant or placebo will be administered orally after the 1st and 3rd WNE, 30 minutes before the participant's habitual bedtime. If the participant well tolerates 10mg, the dose will be increased to 20mg at the 2nd administration. Participants will have continuous access to research nurses during the sleep recording. In the following morning, a nurse will assess possible adverse effects.

Written Narrative Exposure (WNE): We will use a procedure similar to the one used in the R21 study. Sessions will begin at 8PM and approximately 8AM. The morning sessions will not start until the participant's alertness level reaches the level he/she indicated in the morning after the baseline PSG recording. The participant will sit at a desk in a private room with a facilitator, and a pulse transducer will be attached to the distal of the middle finger of his/her non-dominant hand placed on the desk. After a 10-minute acclimatization period, a 5-minute baseline pulse recording will begin. At the end of the baseline, the facilitator will provide instructions to write in as much detail as possible about his/her index trauma including what

happened, how s/he felt, and what s/he perceived and thought and to use the entire 30 minutes. The facilitator will also instruct the participant to orally report an overall level of distress on a scale from 0 – 100 [subjective units of distress scale (SUDS)] at baseline, every 10 minutes, and at the end of the writing period. The facilitator will remain in the same room during the writing to obtain SUDS scores and to assist and encourage the participant if necessary. At the end of the writing period, if warranted, the facilitator will instruct the participant in relaxation techniques for ≤10 minutes. Participants will not be dismissed until distress is minimal.

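### The SAP has no rule for missing nights, and a conventional repeated-measures ANOVA for Hypothesis 1a would drop up to 16 of about 70 participants who have a first treated night

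*SAP*

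**What the plan says.** The SAP (Data Analysis Plan, Hypothesis 1a) compares the arms on "sleep parameters measured at 3 time points (baseline, post-Session 1, and post-Session 3). A repeated-measures ANOVA will be performed", looking for a Group x Time interaction on N3, WASO and REM sleep. Comparisons at single nights are conditional on that test: "If a significant interaction effect is found, group comparisons will be performed at each time point".

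The SAP's only general data-handling sentence covers errors, outliers, normality and transformation. Neither document mentions missing nights, imputation or an analysis set. The only exclusion rule is for pulse segments with artifacts (Protocol, Pulse rate).

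Participants are "randomly assigned to either suvorexant or placebo before the 1st WNE" (Protocol, Study Medication Administration). Sleep change is computed from "respective measures obtained during sleep following the 1st and 3rd WNE sessions" (Protocol, Sleep recordings). For retention, the Feasibility section expects that about "70 of them would complete at least first two WNE sessions", and then "we estimate that 54 participants (27 in each group) would complete the entire protocol". The SAP's power section works from the 54.

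**The concern.** The first treated night lies between Sessions 1 and 2, so everyone who completes Session 2 should have a baseline night and a treated night. A conventional repeated-measures ANOVA needs all three nights from each person. Anyone who leaves before the post-Session 3 recording therefore contributes nothing to the interaction test, although two of their three nights were recorded after consent, and one of them on assigned treatment. The conditional follow-up at post-Session 1 could use those data, but only once the reduced test is significant.

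What is at stake is mainly precision in a small trial. Selection on completion is a second, unproven risk. N3 is also tested under Hypothesis 1a, but the SAP leaves it out of the power evaluation because its expected effect is small, so adequate power for the other outcomes does not cover it. With no rule written down, the handling of missing nights could also be settled after the data are seen.

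**Working it through.** **1. Counts (Protocol, Feasibility).** The plan's own figures reproduce: 40 months x 3.5 per month = 140 enrolled, and about half of 140 = 70 completing Sessions 1 and 2. Then 70 - 54 = 16, and 16/70 = 22.9%.

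Sixteen is an upper bound. The 54 complete the entire protocol, which runs beyond the last sleep recording: "The 1-week CAPS will be administered before the 1st and 3rd sessions and at 1-week follow-up". Anyone lost after the post-Session 3 night stays in the ANOVA. If half of the 16 leave that late, the loss is 8/70 = 11.4%. The base of 70 is Session 2 completers, so 23% is not the loss among all randomised.

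**2. Standard error at post-Session 1.** With n people having all three nights and 70 having the first two, the mixed-model SE relative to the ANOVA SE is sqrt(n/70):
- n = 54: sqrt(54/70) = 0.878, a 12% reduction.
- n = 62: sqrt(62/70) = 0.941, a 6% reduction.

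**3. Standard error at post-Session 3.** Assume equal correlation rho between nights and unit variance; the documents give no rho. The variance of the change from baseline is 2(1 - rho). The part not predictable from the first two nights is 1 - 2rho^2/(1 + rho). Let s be the second divided by the first. The variance ratio is s + (1 - s)(n/70).

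At rho = 0.5, s = 0.667. With n = 54 the ratio is 0.667 + 0.333 x 0.771 = 0.924, and its square root is 0.961.

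**4. Noncentrality of the Group x Time test.** This is the quadratic form of the two change contrasts in their inverse covariance, mixed model divided by completers.

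| Complete + leavers | rho | SE ratio, post-Session 3 | Noncentrality ratio, first-night-only or equal effect | Noncentrality ratio, second-night-only effect |
|---|---|---|---|---|
| 54 + 16 | 0.3 | 0.955 | 1.233 | 1.043 |
| 54 + 16 | 0.5 | 0.961 | 1.229 | 1.026 |
| 54 + 16 | 0.7 | 0.966 | 1.226 | 1.014 |
| 62 + 8 | 0.3 | 0.978 | 1.102 | 1.021 |
| 62 + 8 | 0.5 | 0.981 | 1.100 | 1.013 |
| 62 + 8 | 0.7 | 0.983 | 1.098 | 1.007 |

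**5. Which rho the SAP implies.** The power section gives total N of 16, 22 and 50 for f = 0.37 (absolute value), 0.32 and 0.22. I used noncentrality f^2 x N x 3/(1 - rho), df 2 and 2(N - 2), alpha 0.05, 80% power and even N:
- N = 50 implies rho of 0.27 to 0.295.
- N = 22 implies rho of 0.35 to 0.41.
- N = 16 implies rho of 0.39 to 0.47.

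No single rho fits all three. The N = 50 range belongs to the smallest effect, f = 0.22.

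**6. Completer power at N = 54.** For f = 0.22 and rho = 0.28, noncentrality is 0.0484 x 54 x 3/0.72 = 10.89, which gives power 0.838 (0.832 to 0.846 over rho 0.27 to 0.295). At rho = 0.27, f = 0.32 gives 0.992 and f = 0.37 gives 0.999.

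**7. Simulation.** Settings were f = 0.22, rho = 0.28, 15,000 replicates and dropout at random. The ANOVA was compared with an unstructured likelihood model using a Hotelling-type small-sample reference, as a stand-in for Kenward-Roger.

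| Complete + leavers | Effect on | ANOVA power | Mixed-model power |
|---|---|---|---|
| 54 + 16 | first night | 0.837 | 0.897 |
| 54 + 16 | both equally | 0.839 | 0.896 |
| 54 + 16 | second night | 0.835 | 0.833 |
| 62 + 8 | first night | 0.886 | 0.908 |
| 62 + 8 | both equally | 0.889 | 0.910 |
| 62 + 8 | second night | 0.887 | 0.881 |

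Type I error at 54 + 16 was 0.048 for the ANOVA. For the likelihood model it was 0.057 with an uncorrected chi-square and 0.046 with the small-sample reference. At 62 + 8 the three values were 0.053, 0.059 and 0.050. The small-sample correction is therefore needed.

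**The case against.** The strongest reply is that attrition is already absorbed. The SAP plans on 54 completers, and at that number power is at least 0.99 for the two larger effects and above 0.80 for the smallest. That is true, so this is not a shortfall in planned power. It does not cover N3, and it is no reason to discard recorded nights.

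The simulated gain is also shown at one correlation, the least favourable of those implied. At rho of 0.35 to 0.47, completer power for f = 0.22 is already 0.875 to 0.934, so there is less to gain. This stands.

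The post-Session 1 follow-up is not expressly limited to completers, so the 12% may be available there without any change. This stands in part, because that comparison is run only after a significant interaction.

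On bias, the Feasibility section reports "Reasons for dropouts from the R21 study included time conflicts and a family emergency". Those dropouts come from an earlier study for which no suvorexant arm is described, so they say little about differences between arms here. On the other side, Study Medication withholds the second administration after significant adverse events, which it calls rare. That is a possible treatment-related route to a missing or untreated second night. A mixed model would not by itself settle how to analyse such a night.

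Finally, the same gap affects the CAPS and Session 3-4 pulse ANOVAs under Hypothesis 1b. That widens the point rather than weakening it.

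**Conclusion.** The concern holds, as an improvement that should be made rather than an error that invalidates the analysis. Between 8 and 16 of about 70 participants with a first treated night (11% to 23%) would be left out of the Hypothesis 1a interaction test; the lower figure assumes that half of the 16 leave only after the post-Session 3 night. Using their data cuts the first-night SE by 6% to 12% and the second-night SE by about 2% to 5%. Noncentrality rises by about 10% to 23% for a first-night or equal effect, but by only 1% to 4% for a second-night-only effect, where power does not improve. The gain is therefore least on the night when the Protocol allows a higher dose.

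This rests on four things: complete-case handling, which is inferred from the named method because the SAP does not state it; feasibility projections of about 70 and 54; equal correlation with an assumed rho; and dropout at random. Confidence is medium.

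**What to change.** - State in the SAP how missing nights are handled and define the analysis set. Say also how a second night recorded without the second administration is analysed.
- Make the primary sleep analysis a likelihood-based linear mixed model in all randomised participants by assigned arm, using every available night. Include baseline as one of the outcome visits, with group, visit, group x visit and gender, an unstructured covariance, and a small-sample degrees-of-freedom method such as Kenward-Roger.
- Keep the completer repeated-measures ANOVA as a sensitivity analysis.
- Report dropouts by arm and reason.

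The cost is SAP wording, standard software and slightly more analysis work, with no added participants or visits. The model assumes nights are missing at random, so it addresses selection only under that assumption and recovers precision only in part. If the effect is confined to the second night, the small-sample correction leaves power unchanged or trivially lower (0.881 against 0.887 in the case with 8 leavers).

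### Hypotheses 1a and 1b use the pre-drug value as one of three outcome times; adjusting for it would usually gain power at no data cost, on the SAP's effect scale mainly for REM % and N3

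*SAP*

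**What the plan says.** Under Hypothesis 1a, the SAP's Data Analysis Plan compares the groups on "sleep parameters measured at 3 time points (baseline, post-Session 1, and post-Session 3"). The test is specified so: "A repeated-measures ANOVA will be performed to examine whether there is a Group x Time interaction effect on each sleep parameter of interest", the parameters being N3, WASO and REM sleep. The follow-up rule is "If a significant interaction effect is found, group comparisons will be performed at each time point", which includes baseline.

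Hypothesis 1b reads: "A repeated-measures ANOVA will be performed to examine whether there is a Group x Time interaction effect on CAPS scores". The SAP does not list the CAPS times, but the Protocol does (Design and Overview): "The 1-week CAPS will be administered before the 1st and 3rd sessions and at 1-week follow-up". Under Study Medication Administration in the Protocol, drug or placebo is first given after the first WNE session. The first sleep value and the first CAPS value therefore both precede treatment.

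No covariate is named for either hypothesis. "Baseline CAPS scores will be included as a covariate" appears only under Hypothesis 1c, the mediation analysis. The SAP mentions neither sphericity nor a correction for departures from it.

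Under Power considerations the SAP expects 54 completers (27 per group) and uses α = 0.05. It gives f of 0.37 (in absolute value), 0.32 and 0.22 for WASO, REM minutes and REM %, and states: "A total of 16, 22, and 50 participants are needed to detect a Group x Time effect on WASO and REM sleep" (minutes and percentage). For CAPS it gives f = 0.40 and 12 participants. On N3 it says: "The prior studies suggest small effects of suvorexant on N3; therefore, it was not considered for power evaluation".

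**The concern.** A value taken before the first dose cannot carry a treatment effect. In a Group x Time ANOVA it acts as one arm of a contrast, so all of its noise enters the comparison. Used as a covariate, it removes variance from the post-treatment values and adds noise only through chance imbalance. The Group x Time test is valid when sphericity holds or a correction is applied, so the question is efficiency and not bias.

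On the SAP's own effect scale the gain falls where the plan has least room. REM % has a stated need of 50 against 54 expected completers. N3 is a Hypothesis 1a parameter with no power evaluation, because its effect is expected to be small. The baseline values are already being collected, so any gain costs no data.

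**Working it through.** **Inputs.** From the SAP: N = 54 (27 per arm), α = 0.05, three times, and the f values and sample sizes quoted above. Assumed, because the documents give no figure: the correlation ρ between repeated values, compound symmetry except where stated, and the N3 effect (f = 0.10 or 0.15).

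**1. Which scale is f on?** Read as an interaction f, the planned test has noncentrality λ = f²·N·3/(1−ρ), with 2 and 2(N−2) df. The smallest even N for 80% power equals the SAP's figure when ρ lies in these ranges:

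| Outcome | f | SAP's N | ρ that reproduces it |
|---|---|---|---|
| WASO | 0.37 | 16 | 0.39–0.47 |
| REM minutes | 0.32 | 22 | 0.35–0.41 |
| REM % | 0.22 | 50 | 0.27–0.295 |
| CAPS | 0.40 | 12 | 0.49–0.58 |

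No single ρ gives all of them. The nearest for sleep, ρ of 0.31–0.33, gives 18, 24 and 48. Read instead as a one-night group difference (d = 2f), with ρ = 0.5 and equal effects on both nights, the sleep needs would be 56, 74 and 152. The interaction reading is therefore the one that fits the SAP's figures.

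**2. Noncentrality of the two tests.** Take SD 1 and group differences δ = (0, d₁, d₂).
- Planned: λ = (N/4)·Σ(δⱼ − mean δ)²/(1−ρ).
- Joint: λ = (N/4)·(d₁,d₂)Σ⁻¹(d₁,d₂)ᵀ. Here Σ is the post-treatment covariance given baseline, with diagonal 1−ρ² and off-diagonal ρ−ρ².

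Ratio, joint to planned:
- Equal effects: [2d²/((1−ρ)(1+2ρ))] ÷ [(2d²/3)/(1−ρ)] = 3/(1+2ρ), which is 1.88, 1.50 and 1.25 at ρ = 0.3, 0.5 and 0.7.
- Effect at one time only: 1.5(1+ρ)/(1+2ρ), which is 1.22, 1.13 and 1.06.
- Opposite effects (d, −d): 1.

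Matching the two forms of λ for equal effects gives 3f² = d²/6, so d = √18·f. Thus f = 0.22 means 0.93 SD on both nights, and f = 0.15 means 0.64 SD.

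**3. Power, interaction scale.** The planned test has 2 and 104 df. The joint test is a Hotelling test given baseline with 2 and 50 df. Its λ is multiplied by 1−R², with R² ~ Beta(0.5, 26), to average over chance baseline imbalance. Example, REM % at ρ = 0.5: planned λ = 0.22² × 54 × 3/0.5 = 15.68; joint λ before the imbalance factor is 15.68 × 1.5 = 23.52 for equal effects.

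| Outcome | ρ | Planned | Joint, effect at one time | Joint, equal effects |
|---|---|---|---|---|
| REM %, f = 0.22 | 0.28 | 84% | 89% | 98% |
| REM %, f = 0.22 | 0.5 | 95% | 96% | 99% |
| N3, f = 0.15 | 0.3 | 51% | 57% | 77% |
| N3, f = 0.15 | 0.5 | 66% | 69% | 82% |
| N3, f = 0.10 | 0.3 | 25% | 28% | 42% |

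WASO, REM minutes and CAPS have planned power of 99% or more at ρ of 0.3 or above. There is little or no gain in two settings: ρ = 0.9 with f = 0.10 (95% to 95–96%), and opposite effects (REM % at ρ = 0.3, 85% to 83%).

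**4. Power, one-night scale (d = 2f), ρ = 0.5.** With equal effects: WASO 80% to 92%, REM minutes 67% to 82%, REM % 36% to 49%, CAPS 86% to 96%. With an effect at one time only: WASO 79.7% to 82.5%, CAPS 85.9% to 88.2%.

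**5. Without sphericity** (simulation, 20,000 trials per cell). Under the null, the uncorrected planned test rejects 4.9–5.0% under compound symmetry and 5.1–6.4% in six non-spherical cases. Greenhouse-Geisser gives 4.5–5.1% and the joint test 4.9–5.3%. Power at d = 0.64, corrected ANOVA to joint test:

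| Correlations (baseline–1, baseline–2, 1–2) | Equal effects | Late effect only |
|---|---|---|
| 0.3 / 0.3 / 0.6 | 52% to 66% | 56% to 72% |
| 0.5 / 0.5 / 0.7 | 67% to 74% | 74% to 84% |
| 0.6 / 0.4 / 0.6 | 65% to 78% | 65% to 71% |
| 0.7 / 0.7 / 0.9 | 87% to 85% | 97% to 99.8% |
| all 0.5; SDs 1, 1, 1.5 | 46% to 69% | 44% to 36% |

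**The case against.** The strongest reply is that nothing is broken. On the scale that fits the SAP's figures, the planned test already meets the 80% target for every outcome the SAP powers, and the SAP claims adequacy only for medium to large effects. The larger REM % gain needs ρ near 0.28; at ρ = 0.7 power moves only from 99.7% to 99.7–99.9%. The N3 gain rests on an assumed effect: f = 0.15 is a 0.64 SD difference, which sits awkwardly with an effect called small, and at f = 0.10 N3 stays underpowered under either test. The emphasis on REM % and N3 also depends on reading f as an interaction effect, whereas the SAP describes the sleep values as effects of one night of drug. On that other reading the gains are spread across outcomes. Finally, the joint test can lose power.

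All of this stands as a limit on the size of the point, and it rules out calling the plan wrong. It does not remove the case for the change. The interaction reading is the only one near the SAP's sample sizes, and on the other reading the gain is larger for WASO and REM minutes. A late-only CAPS effect is plausible, since the Protocol reports that most participants in the preliminary study remitted only after the second pair of sessions; the compound-symmetry gain would then be at the small end. Opposite effects on the two nights are hard to expect when the same drug is given on both.

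**Conclusion.** The point holds as an optional improvement, not an error. Under compound symmetry the joint test never has lower noncentrality than the planned one; its only costs are residual degrees of freedom and chance baseline imbalance. On the SAP's apparent scale the gain is about 1 to 14 points for REM % (ρ of 0.28 to 0.5) and about 3 to 26 points for N3 at an assumed f of 0.15 (ρ of 0.3 to 0.5). It is practically nil for WASO, REM minutes and CAPS. Near ρ = 0.9 there is no useful gain, and among the non-spherical cases simulated the worst result was a loss of 8 points. These sizes rest on an assumed ρ, an assumed N3 effect, and an inferred scale for f. The missing sphericity correction is a smaller matter: null rejection reached at most 6.4% in the cases tried.

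**What to change.** For each sleep parameter and for CAPS, amend the Data Analysis Plan as follows.

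- Model the two post-treatment values jointly, with the pre-treatment value as covariate (its own slope at each time) and an unstructured covariance. Test the group effect over both times on 2 df. In complete data this is the Hotelling test above, with 2 and 50 df. Keep the two times as separate outcomes: averaging them would lose power if only one night responds.
- Gender, the randomisation stratum, may be added; the lost degree of freedom changes power by 0.1 point or less.
- Report the adjusted group difference and 95% confidence interval at each post-treatment time whether or not the joint test is significant, labelled as estimates so that no unprotected tests are added.
- Omit the baseline comparison from the follow-up tests.
- Leave the pulse-rate analyses as planned.
- If the ANOVA is kept, name a sphericity correction such as Greenhouse-Geisser.

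The cost is SAP wording and one covariate degree of freedom (two with gender), with no new data. The risk accepted is slightly lower power for opposite-direction effects or ρ near 0.9, and a possible loss under some non-spherical covariances.
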